### 3) Integrated Analysis with Clinical Data

Clinical data will be utilized to stratify or classify patient groups, and sequencing results will be integrated to identify disease-specific gut bacteria.

### \* Observational Items, Clinical Examination Items, and Observation Methods

- Basal characteristics (age, gender, chief complaints, weight, past medical history, present illness, family history, alcohol consumption, smoking history)
- Hematological and serological/immunological markers (complete blood count results, serum alkaline phosphatase, AST, ALT, gamma-GT, total bilirubin, glycated hemoglobin, fasting blood glucose, lipid profile, IgM, IgG, antinuclear antibodies, anti-smooth muscle antibodies, anti-mitochondrial antibodies, HBsAg, HBeAg, HBcAg, HBs-Ab, anti-HBe, anti-HCV status)
- Imaging findings (CT scan, MRI, abdominal ultrasound, endoscopic retrograde cholangiopancreatography (ERCP) if applicable)
- Histopathological findings (pathological findings of liver biopsy tissue if applicable)

### 4) Statistical Analysis Methods

Statistical analysis for the results of microbial species and distribution will involve Taxonomic profiling using the Galaxy platform, followed by LDA analysis. Grouping by primary diagnosis and deriving LDA Effect Size or utilizing MaAsLin2 functionality to identify taxa showing significant compositional changes between diseases. For transcriptome and metabolome results, categorical variables will be analyzed using the Chi-square test, while continuous variables will undergo t-tests. Correlation analysis will employ Pearson's coefficient.

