#### ■ The Utility of Gut-Liver Axis Research for Chronic Intractable Liver Diseases

- ▷ The gut-liver axis refers to bidirectional communication between the liver and gastrointestinal tract mediated by various signaling molecules and cellular pathways. The gut microbiome can regulate liver function and metabolism through the production of diverse metabolites such as short-chain fatty acids and bile acids. Conversely, the liver generates bile secreted into the intestine to aid in fat digestion and absorption, and bile acids also act as signaling molecules that can modulate gut microbiota and intestinal immune function.
- ▷ Dysregulation of the gut-liver axis has been implicated in the onset of non-alcoholic fatty liver disease (NAFLD) and inflammatory bowel disease (IBD), and understanding the underlying mechanisms mediating this interaction could lead to the development of novel therapies targeting specific pathways associated with the gut-liver axis.
- ▷ Therefore, this study aims to identify specific gut microbiome profiles unique to patients with chronic intractable liver diseases and to conduct gut-liver axis research related to etiology and disease progression.

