#### 2. Data collection method

We will collect a total of 20cc of venous blood and 5cc of stool (using a stool collection kit) from each consenting participant (patients and cohabitants living together) at three time points: at the time of the patient's disease diagnosis, 3-6 months after the patient's disease treatment, and 6-12 months after the patient's disease treatment.

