### 3. Selection and Exclusion Criteria for Study Participants (Samples), Target Sample Size, and Justification

#### A. Selection Criteria

Adults aged 19 years and older diagnosed with autoimmune hepatitis, primary biliary cholangitis, primary sclerosing cholangitis, non-alcoholic fatty liver disease, or liver abscess, who have consented to participate in this study at Chungnam National University Hospital.

Adults aged 19 years and older, who are cohabitants of patients diagnosed with autoimmune hepatitis, primary biliary cholangitis, primary sclerosing cholangitis, non-alcoholic fatty liver disease, or liver abscess, and have consented to participate in this study at Chungnam National University Hospital.

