#### C. Sample Size and Justification

##### 1) Sample Size: Total of 3,000 cases

Autoimmune Liver Diseases (patients diagnosed with autoimmune hepatitis, primary biliary cholangitis, primary sclerosing cholangitis): Experimental group 500 cases, Cohabitants control group 500 cases.

Metabolic Liver Diseases (patients diagnosed with non-alcoholic fatty liver disease): Experimental group 500 cases, Cohabitants control group 500 cases

Infectious Liver Diseases (patients diagnosed with liver abscess): Experimental group 500 cases, Cohabitants control group 500 cases

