##### 2) Justification:

The calculation of the sample size was conducted using G\*Power (version 3.1.9.7) to enable comparative studies among patient groups with statistical significance. For this study, we aimed for an effect size of 0.25, significance level  $\alpha$  error probability of 0.05, and power (1- $\beta$  error probability) of 0.95. This calculation resulted in a required sample size of 417 cases per group, totaling 834 samples. Considering a potential loss rate of 20% in the collection of the primary sample, feces, we aimed for 500 cases per group, resulting in a total of 3,000 samples across the three liver disease groups.

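### The one microbiome contrast the protocol names, between diseases, does not match its aim of patient-specific profiles or its cohabitant control group

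*Protocol*

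**What the plan says.** All places are in the protocol.

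- **Aim** (section 1, on the gut-liver axis): "this study aims to identify specific gut microbiome profiles unique to patients with chronic intractable liver diseases".
- **Groups** (section 3.C.1): for each of the autoimmune, metabolic and infectious categories, "Experimental group 500 cases, Cohabitants control group 500 cases".
- **Sampling** (section 2): blood and stool are taken "from each consenting participant (patients and cohabitants living together) at three time points".
- **Sample size justification** (section 3.C.2): the calculation is made "to enable comparative studies among patient groups with statistical significance". It gives a "required sample size of 417 cases per group, totaling 834 samples", and then "we aimed for 500 cases per group, resulting in a total of 3,000 samples across the three liver disease groups".
- **Microbiome analysis** (section 4, item 4): "Grouping by primary diagnosis and deriving LDA Effect Size or utilizing MaAsLin2 functionality to identify taxa showing significant compositional changes between diseases". The diagnoses are the five of section 3.A: participants "diagnosed with autoimmune hepatitis, primary biliary cholangitis, primary sclerosing cholangitis, non-alcoholic fatty liver disease, or liver abscess".

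The remaining sentences of section 4, item 4 assign chi-square tests, t-tests and Pearson correlation without saying which groups are compared. No section states a microbiome comparison of patients with cohabitants.

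**The concern.** A profile can be called unique to patients only by comparison with people who are not patients. The protocol recruits such people, labels them controls and collects their stool. When it comes to the analysis, however, the contrast it names is between one disease and another.

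The two contrasts answer different questions and can disagree in both directions. A change common to all the liver diseases is invisible when diseases are compared only with each other. A difference that comes from the household, such as diet or a shared environment, looks like a disease difference unless cohabitants are in the comparison. Separating these two cases is the reason to have household controls.

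**Working it through.** **1. Reproduce the plan's figure.** Inputs from section 3.C.2: effect size 0.25, alpha 0.05, power 0.95. Read as a standardised mean difference d in a two-sided comparison of two independent groups, the normal approximation is

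n = 2(z₀.₉₇₅ + z₀.₉₅)² / d² = 2(1.960 + 1.645)² / 0.0625 = 416 per group.

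The exact t-test needs 417 (power 0.9501), so 834 in total. The plan's figure is reproduced.

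**2. What that figure shows.** It is a two-group calculation. It fits patients versus cohabitants within a category, and equally one disease group versus another. The total adds only this:

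- 3 categories × 2 groups × 500 = 3,000;
- patient groups alone: 3 × 500 = 1,500.

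So cohabitants are counted as groups of equal size. The calculation does not say which pair of groups was meant, and the justification's own words refer to patient groups.

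**3. Participants outside the named contrast.** 3 × 500 = 1,500 cohabitants, and 1,500 / 3,000 = 50%.

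**4. Taxon shifted alike in every disease.** Illustration: one taxon, normal data, 0.25 SD higher in all patients than in cohabitants, 500 × 0.8 = 400 per group after the plan's 20% loss.

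- Between diseases: all patient means are equal, so the noncentrality is zero and the test rejects at alpha, by construction.
- Patient versus cohabitant in one category: noncentrality = 0.25 × √(400/2) = 3.54, power 0.942.

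**5. Taxon shared with the household.** The taxon is 0.25 SD higher in fatty-liver patients and equally higher in their cohabitants.

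- Between diseases, 400 shifted patients against 800 others: noncentrality = (400 × 800 / 1,200) × 0.25² = 16.67. A one-way ANOVA rejects with probability 0.923 over the five diagnoses, however the autoimmune 400 divide, or 0.963 over the three categories.
- Patient versus cohabitant: the difference is zero, so the test rejects at alpha, by construction.

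**6. How far these figures go.** They concern one taxon without multiplicity correction. With an assumed 100 taxa and a Bonferroni correction (alpha 0.0005), 0.942 falls to about 0.52. They also treat household members as independent. With 400 complete pairs and an assumed within-household correlation of 0.3, d_z = 0.25 / √(2 × 0.7) = 0.211, and the two powers become 0.988 and 0.762. If fewer cohabitants take part, for instance 300 or 200 against 400 patients (independent groups, alpha 0.05), power is 0.905 or 0.822.

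**The case against.** The strongest reply is that this is an omission which a statistical analysis plan would fill. The methods paragraph is short, does not claim to be exhaustive and does not exclude cohabitants, and the control label in section 3.C.1 already tells the reader what they are for. Silence alone would indeed be no finding. But the paragraph is not silent: it names a contrast, and that contrast cannot deliver the stated aim.

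One might also treat cohabitants as a no-diagnosis level of the grouping variable. The text does not say so, and it describes the target as change between diseases. If that was the intention, one sentence would settle it.

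A third reply is that the effects in steps 4 and 5 are built into the scenarios. That is true of the alpha-level results, which follow by definition. The scenarios show what the named contrast can and cannot separate; they do not estimate how often such taxa occur.

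Two stronger readings should be resisted. A reader might infer that the sample size proves the patient-cohabitant contrast was the powered one, because 834 is a two-group total and 3,000 requires the cohabitants. It does not: two disease groups compared pairwise give the same 417 and 834. A reader might also infer that the protocol leaves cohabitants out of all analysis. It does not say that; the tests for transcriptome and metabolome data name no groups at all.

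**Conclusion.** The point holds as a mismatch within the protocol. The named microbiome contrast fits neither the aim in section 1 nor the control design in section 3.C.1.

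The size that rests on the document alone is 1,500 of 3,000 targeted participants in no named microbiome contrast. The 94% and 92% are single-taxon illustrations that assume normal data, a 0.25 SD shift, independent groups and no multiplicity correction. They are not the power of a taxon-wide analysis.

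This should be fixed, but it does not threaten the data: the planned stool samples can answer the aim, and the contrast can be corrected at any time before analysis.

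**What to change.** - In section 4, item 4, add patient versus cohabitant within each disease category as the microbiome contrast that answers the aim. Keep the between-disease contrast alongside it.
- Fit it in MaAsLin2, which is already named, with a household random effect. This respects the shared household and keeps patients enrolled without a cohabitant, which section 5.B allows.
- State the time point. Either use the samples taken at diagnosis, or, if the three time points of section 2 are pooled, add a participant random effect as well. A household effect alone does not handle repeated samples from one person.
- In section 3.C.2, align the reference to patient groups with the comparison that the calculation is meant to support.

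The sample size and the sampling schedule do not change. The cost is wording in two sections and modest analysis work.

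### The stated taxon test looks for differences between diseases, which does not show which disease is altered and so cannot by itself yield disease-specific bacteria

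*Protocol*

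**What the plan says.** Protocol section 4, item 4 (Statistical Analysis Methods) sets the taxon analysis: "Grouping by primary diagnosis and deriving LDA Effect Size or utilizing MaAsLin2 functionality to identify taxa showing significant compositional changes between diseases". Item 3 of the same section (Integrated Analysis with Clinical Data) states the product: "sequencing results will be integrated to identify disease-specific gut bacteria". The Background, under the gut-liver axis heading, says "this study aims to identify specific gut microbiome profiles unique to patients with chronic intractable liver diseases".

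Section 3.C plans 500 patients and 500 cohabitant controls in each of three categories (autoimmune, metabolic, infectious). The taxon analysis does not mention the cohabitants. The protocol names no reference disease, no pairwise or one-against-rest rule, and no rule for assigning a taxon to a disease.

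**The concern.** The test and the conclusion have different null hypotheses. A test between diseases asks whether all diseases are equal, or whether a disease equals a reference disease. A claim that a bacterium is specific to one disease needs more: that disease must be the one that departs, both from normal and from the other diseases.

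If no rule is set, the tools' own outputs tend to fill the gap. Multi-class LDA Effect Size labels a taxon with the class of highest mean. A taxon depleted in one disease then carries the name of another disease that has not changed. MaAsLin2 with diagnosis as a factor gives coefficients against one reference disease. A taxon altered only in that reference then looks altered in every other disease. At stake is the study's main product, the list of bacteria attributed to each disease.

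**Working it through.** **Inputs.** From section 3.C: "we aimed for an effect size of 0.25", alpha 0.05, power 0.95, "required sample size of 417 cases per group, totaling 834 samples", and a "potential loss rate of 20" per cent. The type of effect size and the sidedness are not named.

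**The plan's own figure.** Two-sided two-sample comparison with standardised difference d = 0.25:
- Normal approximation: n = 2(1.960 + 1.645)² / 0.25² = 2 × 12.996 / 0.0625 = 415.9, so 416 per group.
- Noncentral t: 417 per group (power 0.9501; 416 gives 0.9496).

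The 417 is reproduced, so 0.25 is read as d, in SD units. Evaluable patients per category: 500 × (1 − 0.20) = 400. A single two-group contrast at 400 per group has power 0.942.

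**Assumptions for the simulation.** These are not in the protocol: log-normal abundance with SD 1 on the log scale; tests at unadjusted 0.05; an LDA score cut-off that removes none of these taxa; rank tests or a linear model standing in for MaAsLin2 coefficients. How the two tools label taxa is general knowledge of the methods.

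**One category of three shifted by 0.25 SD, 400 per category.**

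| Scheme | Depleted in one disease | Enriched in one disease |
|---|---|---|
| Kruskal-Wallis, label = highest mean | 96% significant; unaffected diseases named in 47% and 48%, altered one in 0% | altered disease named in about 95%, a wrong one in under 1% |
| The same, strict all-pairs option | about 3% declared at all | about 3% declared at all |
| Reference-coded model, altered disease as reference | each unaffected disease flagged in 93-94% | at least one unaffected disease flagged in 98% |
| Reference-coded model, unaffected disease as reference | altered disease 94%, other unaffected disease 5% | altered disease 93%, other unaffected disease 5% |

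At a depletion of 0.5 SD the pattern sharpens: the highest-mean label goes to the unaffected diseases in about 50% each, and with the altered disease as reference each unaffected one is flagged in 100%.

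**Would between-disease contrasts alone repair it?** Take the rule: differs from both other categories in the same direction. With one altered category it names that category in 89% and each unaffected one in 2-3%. But rank tests do not change under a common shift, so means (−0.25, −0.25, 0) are indistinguishable from (0, 0, +0.25). When two categories are depleted and the third is normal, the rule names the normal one in about 88%. Patients alone cannot settle which category has moved.

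**Adding the cohabitants.** Also require a difference in the same direction from the category's own cohabitants (400 per group, treated as unpaired):
- Two categories depleted: the normal third is named in about 2% instead of 88%.
- One category altered: it is named in about 85-86%. As a rough check, independence would give 0.89 × 0.942 = 0.84. The contrasts share the altered group's sample, so the joint figure is a little higher.

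**The case against.** The protocol never says that an LDA Effect Size label or a MaAsLin2 coefficient will be read as specificity. The statistical section claims only changes between diseases, which those tools do test; the stronger term stands under a separate integration step. The reference level, tool options and follow-up contrasts are details that an analysis plan, not shown here, may settle.

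This stands in part. Missing settings are no finding. But the protocol itself fixes the tools, the grouping and the contrast, and promises a conclusion that this contrast does not test. An analysis plan that followed it literally would inherit the mismatch.

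A reader might infer two stronger things, and neither is supported:
- *That taxa are routinely credited to the wrong disease.* Enriched taxa under LDA Effect Size and MaAsLin2 with an unaffected reference are mostly attributed correctly, and the strict all-pairs option mostly loses taxa rather than mislabelling them.
- *That the Background commits the study to bacteria unique to one disease as against the others.* Its wording contrasts patients with people who do not have these diseases. The commitment rests on the integration section alone.

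The rates are also illustrative, since no false-discovery correction or effective LDA cut-off was applied. A correction lowers how often a taxon is declared, but not which disease is then named.

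**Conclusion.** The concern holds as a mismatch between stated test and stated conclusion: a between-disease hit does not show which disease is altered. Misattribution is near certain in two situations: a taxon depleted in one disease under highest-mean labelling, and a taxon altered in the MaAsLin2 reference disease. Elsewhere it is small.

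Overall frequency depends on facts that the protocol cannot give. If enrichment and depletion were equally likely, about half of LDA Effect Size hits on singly altered taxa would be miscredited. If the reference were arbitrary among three categories, about one third of altered taxa would be under MaAsLin2. Both are assumptions. All these rates also rest on exactly one altered category.

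The point should be settled before analysis because it governs the main output. It does not invalidate the data collection.

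**What to change.** Add to section 4, item 4, a definition along these lines: *A taxon is called specific to a disease category only if (a) it differs from that category's own cohabitant controls and (b) it differs in the same direction from each of the other two categories, in multiplicity-adjusted MaAsLin2 contrasts. It is reported as enriched or depleted in that category. All other significant taxa are reported as differing between diseases, with no disease named.* State also that neither the LDA Effect Size class label nor a single reference-level coefficient will be used for attribution.

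The cost is wording, refits of the same model with each category as reference, and the cohabitant contrasts. No new samples are needed. Power at 0.25 SD falls from about 94% for one contrast to about 85-86% for the combined rule (400 per group, unadjusted 0.05, cohabitants unpaired). It will be lower after multiplicity adjustment, and lower with fewer cohabitants, which is likely because section 5.B lets patients enrol without one.

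Apply the rule to the three categories. With five separate diagnoses and an assumed equal split of the autoimmune group (400 / 3, about 133 each), condition (b) alone, extended to all four other diagnoses, would detect a 0.25 SD change in only 31-38% of runs.

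### The protocol lets the disease-specific taxa come from either LDA Effect Size or MaAsLin2 and names no primary tool, so the list may rest on contrasts not adjusted for recorded covariates

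*Protocol*

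**What the plan says.** The taxon analysis is in Protocol section 4, part 4 (Statistical Analysis Methods). It begins with "Taxonomic profiling using the Galaxy platform, followed by LDA analysis", continues with "Grouping by primary diagnosis", and ends in a choice of two tools: "deriving LDA Effect Size or utilizing MaAsLin2 functionality to identify taxa showing significant compositional changes between diseases". No rule says which tool is primary, how to choose between them, or what to do if they disagree. Nothing elsewhere in the protocol settles the choice.

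Other sections describe a design with more structure than that sentence uses:

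- Section 2 takes samples "from each consenting participant (patients and cohabitants living together) at three time points".
- Section 3.C.1 plans, for each of three disease groups, "Experimental group 500 cases, Cohabitants control group 500 cases".
- Section 5.B allows a patient to be enrolled without a cohabitant, so some households have one member.
- The list of observational items in section 4 includes age, sex, weight, alcohol use and smoking.
- Section 4, part 3 (Integrated Analysis with Clinical Data) says only this about the use of clinical data: "Clinical data will be utilized to stratify or classify patient groups". It states no adjustment model.

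**The concern.** The documents do not describe the two tools, so the following is general knowledge of the methods. LDA Effect Size screens taxa with rank tests between classes and ranks them by a discriminant score. An optional subclass gives crude stratification, but there is no covariate regression and no random effect. MaAsLin2 fits one regression per taxon and accepts covariates, random effects and false-discovery control. The two are not interchangeable for a study with repeat samples, household controls and recorded covariates.

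The study's aim (section 1) is to find microbiome profiles specific to chronic liver diseases. The same section links the microbiome to obesity and diabetes, says that diet and lifestyle change its composition, and gives weight loss and lifestyle change as current treatment for fatty liver disease. If the disease groups differ in such factors, an unadjusted contrast between diseases mixes them with the disease. What is at stake is whether a reported taxon can be read as disease-specific.

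**Working it through.** **1. The plan's own figure.** Section 3.C.2 gives an effect size of 0.25, alpha 0.05, power 0.95 and 417 per group (834 in total). Reading 0.25 as a standardised mean difference d with a two-sided test:

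n = 2 × (1.960 + 1.645)² / 0.25² = 2 × 12.995 / 0.0625 = 415.8, so 416. The exact noncentral t calculation gives 416.8, so 417.

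The figure is reproduced. It belongs to an unadjusted two-sample t-test at one time point, so the sample size section does not indicate which microbiome tool is meant. With 500 per group and the stated 20% loss, 500 × 0.80 = 400 remain. That number is used below.

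**2. Unadjusted confounding (illustration).** Assumed, not in the documents: a covariate differs by 0.5 to 1 SD between two disease groups and has a within-group correlation of 0.2 with a taxon that is unrelated to disease.

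- Spurious d = shift × correlation: 0.5 × 0.2 = 0.10, and 1 × 0.2 = 0.20.
- Test statistic centre = d × √(400/2): 0.10 × 14.14 = 1.41, and 0.20 × 14.14 = 2.83.
- Rejection at two-sided 5%: Φ(1.41 − 1.96) ≈ 0.29, and Φ(2.83 − 1.96) ≈ 0.81.

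These are rates for one taxon before any false-discovery control, comparing two full disease groups. If the three autoimmune diagnoses, which share one group of 500, are analysed separately, each group is smaller and the same spurious d is rejected less often.

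**3. Choosing between two tools.**

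- If the two tests were independent: 1 − 0.95² = 9.75%.
- They use the same data and are strongly correlated. One null, unconfounded taxon was simulated (400 against 400, 70% prevalence, lognormal abundance, 4,000 replicates). A Kruskal-Wallis test rejected 5.2% of the time, a linear model on log abundance 5.0%, and at least one of the two 5.9%.

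**4. Repeat visits, only if the three are pooled as independent samples.** The true level is 2 × [1 − Φ(1.96/√(1 + 2·ICC))], with the within-person correlation (ICC) assumed:

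| ICC | True level |
|---|---|
| 0.3 | 0.12 |
| 0.5 | 0.17 |
| 0.7 | 0.21 |

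**5. Household pairs ignored in a patient-cohabitant contrast.** The true level is 2 × [1 − Φ(1.96/√(1 − r))], with the pair correlation r assumed:

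| r | True level |
|---|---|
| 0.1 | 0.039 |
| 0.3 | 0.019 |
| 0.5 | 0.006 |

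The level falls below 5%, so the cost is power and not false positives. In a contrast between diseases among patients only, no patient-cohabitant pairs arise.

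**The case against.** The strongest reply is that covariates, random effects, the handling of visits and the false-discovery threshold usually belong in the SAP, which is not shown. The protocol nowhere says that analyses will be unadjusted, and it does foresee stratifying or classifying patients by clinical data. The confounding figures rest on assumed values and describe any unadjusted test. MaAsLin2 run without covariates would be biased in the same way. This is largely right, and it limits the point. The full covariate list and the threshold may wait for the SAP. What remains is that the protocol itself offers an open choice for its central analysis, and one option cannot carry a regression adjustment whatever the SAP adds.

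A reader might infer more than the documents support:

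- *That picking the tool afterwards doubles the error rate.* The 9.75% needs independent tests. The simulation gave about 6%.
- *That the repeat visits will inflate error.* This follows only if visits are pooled as independent, which the protocol never states.
- *That ignoring household pairs creates false findings.* It loses power instead.
- *That LDA Effect Size cannot deal with confounders at all.* Subclass stratification is possible, though crude.
- *That the disease groups are known to differ in age, sex or lifestyle.* The protocol gives no such values. Its background only makes differences plausible.
- *That cohabitants are excluded from the taxon analysis.* The text names no contrast that uses them, but does not exclude them. Naming one tool would not by itself settle this.

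**Conclusion.** The point holds in limited form. The protocol permits its list of disease-specific taxa to come from a method that cannot adjust by regression for covariates the study records and cannot model its repeat visits and households. The protocol names no primary endpoint, so the result at risk is the taxon list that is the study's stated aim.

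The main harm is possible confounding, and its size cannot be known from the documents. The 29% to 81% range is an illustration under the assumed shift and correlation. Inflation from the tool choice is secondary, and the repeat-visit inflation of 12% to 21% is conditional on pooling. The plan should be changed because a better-suited method is already named in it and costs little to adopt.

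**What to change.** In section 4, part 4, name MaAsLin2 as the single primary taxon analysis and state its model, since naming the tool alone would not secure adjustment:

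- Fixed effects: disease group (a cohabitant takes the group of the patient in the household), patient/cohabitant status, their interaction, visit, age and sex.
- Random intercepts: participant and household. Patients without a cohabitant enter as single-member households.
- Contrasts: patient versus cohabitant within each disease group, and between diseases among patients. The interaction is needed for both. An additive model would give one pooled patient-cohabitant difference, and its disease effects would mix patients with cohabitants.
- Control of the false-discovery rate. The threshold can be left to the SAP.
- A sensitivity analysis adding weight, alcohol and smoking. They are kept out of the primary model because they may be part of the disease process.
- LDA Effect Size reported as descriptive only.

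The cost is slightly more analysis work, and LDA Effect Size rankings lose inferential status. No further participants, samples or assays are needed, because the covariates and visits are already in the protocol.

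### LDA Effect Size alone may name disease-specific bacteria, although on relative abundances unaffected taxa can appear to change when a common taxon shifts strongly or many taxa fall together

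*Protocol*

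**What the plan says.** Stool is assayed by 16S amplicon sequencing (Protocol, section 4, Analytical Methods). No spike-in, qPCR or cell count is mentioned, so the data are shares of a read total.

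Statistical Analysis Methods then lists taxonomic profiling and LDA analysis, with participants grouped by primary diagnosis. LDA Effect Size or MaAsLin2 is to "identify taxa showing significant compositional changes between diseases". The two tools are joined by *or*, so either is enough to declare a taxon. The section names no normalisation, transformation, log-ratio step or significance threshold.

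The intended conclusion stands under Integrated Analysis with Clinical Data: "sequencing results will be integrated to identify disease-specific gut bacteria".

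On group size, section 3.C states: "required sample size of 417 cases per group, totaling 834 samples". It then adds: "we aimed for 500 cases per group, resulting in a total of 3,000 samples across the three liver disease groups".

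**The concern.** Shares must sum to one. If one common taxon expands, the share of every other taxon falls even where those bacteria are unchanged. If many taxa decline together, the share of every unaffected taxon rises. A test applied to shares cannot tell such an induced change from a real one.

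This is bias rather than noise, so more participants make it more visible instead of averaging it out. The study's main product is a list of bacteria said to be specific to a disease. If the largest real change in a disease is in a dominant taxon, part of that list could be taxa that did not change, and later mechanistic work would start from them.

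**Working it through.** **Group size.** The plan's inputs are effect size 0.25, alpha 0.05 and power 0.95. The two-sided normal approximation gives n = 2(1.960 + 1.645)² / 0.25² = 416 per group. The exact noncentral-t calculation gives 417 (power 0.9501), which is the protocol's figure. With 500 enrolled and 20% lost, 500 × 0.80 = 400 per group, the size used below.

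**Induced change.** If a taxon with share p rises f-fold, every unchanged share is multiplied by 1/(1 + p(f − 1)):

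- p = 1%, f = 2: 1/1.01 = 0.990
- p = 5%, f = 2: 1/1.05 = 0.952
- p = 10%, f = 2: 1/1.10 = 0.909
- p = 20%, f = 2: 1/1.20 = 0.833
- p = 5%, f = 5: 1/1.20 = 0.833
- p = 20%, f = 3: 1/1.40 = 0.714

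For the factor 0.833 at a between-person SD of 1 (natural-log scale), the standardised shift is d = ln(1.20)/1 = 0.182. The noncentrality is 0.182 × √(400/2) = 2.58, and an unchanged taxon is flagged at p < 0.05 with probability 0.73. At SD 2 the shift is d = 0.091 and the probability 0.25.

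**Simulation, first design.** 100 log-normal taxa with multinomial reads, one taxon truly changed, 400 v 400. Share, fold change and SD are assumptions. Entries are the percentage of unchanged taxa flagged, at log-SD 1 / 1.5 / 2.

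| True change | t-test on log relative abundance, p < 0.05 | Same, Benjamini-Hochberg at 0.05 | Rank test plus approximate LDA cut-off |
|---|---|---|---|
| none | 4 / 4 / 5 | 0 / 0 / 0 | 3 / 3 / 4 |
| 1% doubles | 5 / 6 / 6 | 0 / 0 / 0 | 3 / 5 / 6 |
| 5% doubles | 9 / 5 / 6 | 1 / 0 / 0 | 6 / 5 / 5 |
| 10% doubles | 19 / 8 / 6 | 3 / 1 / 0 | 13 / 6 / 5 |
| 20% doubles | 57 / 15 / 10 | 43 / 1 / 1 | 39 / 11 / 6 |
| 20% triples | 97 / 53 / 25 | 97 / 39 / 4 | 75 / 42 / 20 |

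These rates lie below the closed form because the share itself varies between people: for 20% doubling at SD 1 the mean simulated d is 0.150, against 0.182.

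Effect of group size: with a 20% taxon tripling at SD 1.5, 16% of unchanged taxa are flagged at 100 per group and 53% at 400.

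**Simulation, second design.** A taxon at 5% share, 400 v 400, Kruskal-Wallis p < 0.05 on relative abundance (Benjamini-Hochberg at 0.05 in brackets). Ranges span repeated simulations.

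- Five-fold rise: 47% to 70% at SD 1 (34% to 44%); 21% at SD 1.5 (3%); 6% to 11% at SD 2 (0% to 1.5%).
- Three-fold rise: 17% to 19% at SD 1 (1%); 9% at SD 1.5 (0%); 5% at SD 2 (0%).
- Two-fold rise: 9% to 11% at SD 1 (0.2%); 7% at SD 1.5 (0.2%); 5% at SD 2 (0%).

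**Possible remedies.** With a single changed taxon, centred log-ratio values flag only 4% to 8% of unchanged taxa. That is partly built into the scenario: one taxon of 150 rising five-fold moves the log geometric mean by only ln(5)/150 = 0.011.

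If instead 30% of taxa fall to 0.3-fold, the log geometric mean moves by 0.30 × ln(0.3) = −0.361, so every unchanged taxon appears to rise by 0.361. On shares, assuming those taxa hold 30% of reads, the induced rise is smaller: −ln(1 − 0.30 × 0.70) = 0.236. Simulated rates of unchanged taxa flagged in this scenario:

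- rank test on shares: 37% to 74%
- plain centred log-ratio: 58% to 100%
- bias-corrected log-ratio model: 5% to 8%
- bias-corrected model and rank test both required: 3% or fewer, with no loss of power in the simulation

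**The case against.** **The protocol never says relative abundance, and settings belong in the SAP.** This largely stands for MaAsLin2. A reader might infer that both tools, as written, test shares. The text does not support that: no normalisation is fixed for MaAsLin2, a log-ratio run is not excluded, and a SAP that is not at hand may settle it. The absence of such a setting is no error. The objection does not reach LDA Effect Size, which is named, works on shares, and is allowed to decide alone.

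**The stated target is composition.** A lower share is a compositional change, and 16S data alone do not identify absolute abundance. This is fair for the analysis sentence taken alone. The integrated analysis, however, draws a conclusion about bacteria specific to a disease, and an induced change in share is weak support for that.

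**The size depends on favourable assumptions.** This also stands. A reader might infer that many unaffected taxa will be called disease-specific, or that false-discovery correction is of no use. Neither holds in general. With a 5% taxon, correction leaves 3% or fewer flagged at SD 1.5 or more, or for rises of three-fold or less. It fails for a five-fold rise at SD 1, for a 20% taxon doubling at SD 1, and for a 20% taxon tripling at SD 1 or 1.5. Nothing in the protocol shows which case applies. Grouping by primary diagnosis also splits the 500 autoimmune patients among three diagnoses, so those groups will be smaller than 400 and will flag fewer induced changes.

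**Conclusion.** The point holds as a conditional weakness of a named method. LDA Effect Size may by itself declare taxa disease-specific, and on shares it can list taxa that did not change. The same applies to MaAsLin2 only if it is run under total-sum scaling.

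At 400 per group the size runs from about nominal (a 1% to 5% taxon doubling, or a 5% taxon rising five-fold at log-SD 2) to roughly half or more of unchanged taxa (a 5% taxon rising five-fold, or a 20% taxon tripling, at log-SD about 1). High SD alone does not remove it: a 20% taxon tripling still flags 20% to 25% at log-SD 2. Shares, fold changes and SDs are assumptions throughout, and the LDA cut-off was only approximated.

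A reader might also infer that a switch to centred log-ratios would settle the matter. It would not, because that scale is itself biased when many taxa move in one direction. The point is a cheap improvement and does not show that the planned analysis is invalid.

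**What to change.** Add to Statistical Analysis Methods:

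- A taxon is called disease-specific only if it is also significant, after false-discovery correction, in a bias-corrected log-ratio model. LDA Effect Size alone is not sufficient.
- The rule for handling zeros is stated in advance.
- Sequencing depth is compared between groups, because a depth difference changes the number of zeros and can mimic a difference in rare taxa.
- Plain centred log-ratio normalisation is not the sole safeguard.

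Cost: one more analysis of the same data, with no extra samples or assays. The list of taxa will be somewhat shorter, and results will read as log-ratios instead of percentages.
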